## 16. ADVERSE EVENTS

### 16.1. DEFINITION

An adverse event (AE) is any untoward medical occurrence, unintended disease or injury, or untoward clinical signs (including abnormal laboratory findings) in subjects, users or third persons, whether or not related to the investigational medical device.

Abnormal results of diagnostic procedures are considered to be adverse events if the abnormality:

- Is considered by the investigator to be of clinical significance

A serious adverse event (SAE) is defined as any undesired adverse event in a clinical study or performance evaluation study occurring to a subject, users or third persons whether or not related to the investigational medical device that led directly or indirectly to the following:

- Leads to death;
- Results in a life-threatening illness or injury;
- Results in a permanent impairment of a body structure or a body function;
- Requires in-patient hospitalization or prolongation of existing hospitalization;
- Results in medical or surgical intervention to prevent life-threatening illness or injury or permanent impairment to a body structure or a body function;
- Led to foetal distress, foetal death or a congenital abnormality or birth defect

This includes device deficiencies that might have led to a serious adverse event if a) suitable action had not been taken or b) intervention had not been made or c) if circumstances had been less fortunate. Planned hospitalization for a pre-existing condition, or a procedure required by the CIP, without serious deterioration in health, is not considered a serious adverse event.

An adverse device effect (ADE) is any adverse event related to the use of an investigational medical device. This definition includes any event resulting from insufficiencies or inadequacies in the instructions for use or the deployment of the device, or any event that is a result of a user error, or from intentional misuse of the investigational device.

A Serious Adverse Device Effect (SADE) is an adverse device effect that has resulted in any of the consequences characteristics of a serious adverse event or that might have led to any of these

consequences if suitable action had not been taken or intervention had not been made or if circumstances had been less fortunate.

An Unanticipated Serious Adverse Device Effect (USADE) is a serious adverse device effect which by its nature, incidence, severity or outcome has not been identified in the current version of the risk analysis report

A Device Deficiency is any inadequacy of a medical device with respect to its identity, quality, durability, reliability, safety or performance (device deficiencies include malfunctions, use errors, and inadequate labelling).

Anticipated Adverse Events, A list of anticipated adverse events is provided in “Anticipate Risks” section of this study protocol.

## 16.2. ADVERSE EVENTS CLASSIFICATION

The severity of adverse events will be rated as follows:

- Mild: An AE which is transient or mild in nature, which does not limit the subject’s activity, and which does not require medical intervention
- Moderate: An AE which has mild-moderate impact on the subject’s activity or requires minimal medical intervention or monitoring
- Severe: An AE which has marked impact on the subject’s activity or requires medical care

Each AE will be classified as SAE or non-SAE as follows:

- A serious adverse event (SAE) is any adverse event that is fatal or life threatening, or results in permanent impairment of a body structure or function, or in-patient or prolonged hospitalization, or requires medical or surgical intervention to prevent life-threatening illness or injury, or led to foetal distress, foetal death or congenital abnormality or birth defect.

The relationship of the AE and SAE to the treatments or procedures is defined as follows:

- Unrelated: Any event that does not follow a reasonable temporal sequence from administration of study treatment AND that is likely to have been produced by the subject’s clinical state or other modes of therapy administered to the subject.
- Unlikely: Any event that does not follow a reasonable temporal sequence from administration of study treatment OR that is likely to have been produced by the subject’s clinical state or other modes of therapy administered to the subject OR that does not follow a known pattern

of response to suspected device OR does not reappear or worsen when the device is re-administered

- Possibly: Any reaction that follows a reasonable temporal sequence from administration of study treatment OR that follows a known response pattern to the suspected device AND that could not be reasonably explained by the known characteristics of the subject's clinical state or other modes of therapy administered to the subject.
- Related: Any reaction that follows a reasonable temporal sequence from administration of study treatment AND that follows a known response pattern to the suspected device AND that recurs with re-challenge, AND/OR is improved by stopping the use of the device.

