#### **4.6. STEPS THAT WILL BE TAKEN TO CONTROL/ MITIGATE THE RISK**

In order to ensure the safety of the MCS device for subjects enrolled in the study an independent group of experts chosen by the sponsor will constitute the Data and Safety Monitoring Board (DSMB). The DSMB will evaluate every Adverse Event. All Adverse Events will be reported as per the standard clinical practices as detailed in section 16.3. All adverse event incidence rates will be summarized by anticipation, severity and relationship to the investigational device.

In addition, in case of occurrence of a SAE at least possibly related to the MCS the study will be terminated immediately and until completion of the DSMB investigation.

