#### **4.7. RISK/BENEFIT RATIONALE**

The MCS is used in conjunction with a standard colonoscope during a colonoscopy procedure. Hence, the complications associated with using the MCS are anticipated to be similar to those associated with the colonoscopy procedure. As with any colonoscopy procedure, when using the MCS there is some risk of bowel perforation, pain, infection and bleeding. Although the risks of the procedure with the MCS is expected to be comparable to conventional colonoscope (0.35%), the device is an add-on to a standard colonoscope. Hence, diameter is bigger, and the cleansing time may add some minutes to the procedure time. In contrast, a disadvantage that is presented in standard colonoscopy and can possibly be decreased when using the MCS is that of stopping the colonoscopy procedure due to improper preparation of the colon by the subject.

The potential benefits of the MCS are utilization of a cleaning technology that may improve the standard colonoscopy visualization, reduce reliance on subject pre-procedure colon preparation for ensuring high quality colonoscopy, increase the subject compliance to colonoscopy procedure and reduce the need for repeated colonoscopies required due to insufficient colon preparation, these consequently may reduce pain, discomfort, risk and cost.

The latest MCS version was tested in an animal study including 35 pigs and two preliminary clinical studies including 30 subjects. No major complication or serious adverse events occurred within the course of those studies, and only 2 mild adverse events were reported .

In addition, these clinical studies demonstrated an excellent cleansing effectiveness; MCS improved the cleansing level from 30% at baseline to 93% after the cleansing was operated, where preparation was identical to the current study. Efficacy results support the study design rationale that decreases the risks associated with the preparation without increasing the risk related to incomplete colonoscopy procedure.

Lastly, patients to be enrolled to this study shall be eligible to colonoscopy, thus the risks detailed above covers all the population intended to participate in the study (i.e., screening, surveillance and diagnostic).

Considering the residual risks and the potential and the risk against benefit assessment, it can be concluded that the system may offer potential benefit to the patients along with no significant risk increase.

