#### 15.2.3. SECONDARY SAFETY ANALYSIS

The secondary endpoint is to evaluate the Device related adverse event and the overall adverse events rate.

The safety analysis set will consist of all subjects who were enrolled into the study.

Individual listings of adverse events including type of device, adverse events (reported term), seriousness, duration, relationship to the study device, severity and the adverse events outcome will be provided for the total population and per population group.

AEs will be summarized using frequency counts and percentages.

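### Under Section 16.2 an injury of a new type meets both Unlikely and Possibly, cannot be Related on the natural reading, and no rule says which grade applies

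*Combined protocol and SAP*

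**What the plan says.** Section 16.2 of the combined protocol and SAP grades relatedness as *Unrelated*, *Unlikely*, *Possibly* or *Related*.

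- *Unlikely* is a chain of alternatives, any one of which is enough. One alternative is "OR that does not follow a known pattern" "of response to suspected device OR does not reappear or worsen when the device is re-administered"; the second half of that text adds a separate limb on re-administration.
- *Possibly* is met by plausible timing or by a known response pattern, combined with the absence of another reasonable explanation.
- *Related* is "Any reaction that follows a reasonable temporal sequence from administration of study treatment AND that follows a known response pattern to the suspected device", followed by a further condition on re-challenge or improvement on stopping.

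Section 16.1 defines an adverse device effect as an event related to use of the device. It includes user error and inadequate instructions, and it does not ask whether the event has been seen before. An unanticipated serious adverse device effect (USADE) is one "which by its nature, incidence, severity or outcome has not been identified in the current version of the risk analysis report".

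The gradings are used in at least two places. Section 15.2.3 states: "The secondary endpoint is to evaluate the Device related adverse event and the overall adverse events rate". It does not say which grades count as device related. Section 4.6 states that "in case of occurrence of a SAE at least possibly related to the MCS the study will be terminated immediately", pending the DSMB investigation. Under Section 16.3 the DSMB also determines relationship to the device in writing; no separate scale is given for it.

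**The concern.** A relatedness scale should let an assessor recognise harm that nobody has described before. Here, lack of precedent counts against the device twice: it is sufficient for *Unlikely*, and its opposite is necessary for *Related*. For a device that the synopsis describes as not CE marked, unrecognised harms are the ones the safety review most needs to identify.

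Two investigators could grade the same new injury *Unlikely* and *Possibly*, and both would comply with the protocol. Those two grades lie on opposite sides of the Section 4.6 threshold, and may lie on opposite sides of whatever cut defines the device-related rate. For an event that is unanticipated by its nature, the feature that points to the USADE category in Section 16.1 is the same feature that supports *Unlikely* in Section 16.2.

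**Working it through.** The plan states no figure on this point, so there is none to reproduce. The check encodes the Section 16.2 definitions and enumerates them.

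**Inputs.** Five yes/no conditions from Section 16.2: T, plausible timing; K, known response pattern; A, alternative cause; R, recurs on re-challenge; S, improves on stopping. This gives 2^5 = 32 combinations, of which 16 have no known pattern (K = 0).

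**Rules as written.**

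- *Unrelated*: not T, and A.
- *Unlikely*: not T, or A, or not K, or not R (here an untested R counts as not recurring).
- *Possibly*: either T or (K and not A), or (T or K) and not A, depending on where the AND attaches.
- *Related*: the wording "AND that follows a known response pattern to the suspected device AND that recurs with re-challenge, AND/OR is improved by stopping the use of the" … can be parsed as T and K and (R or S), the natural reading, or as (T and K and R) or S, the looser one.

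**Step 1: a new type of event against *Unlikely*.** Not K is enough by itself, so 16 of 16 combinations with K = 0 meet *Unlikely*.

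**Step 2: the same event against *Related*.** On the natural reading, 0 of 16 qualify. On the looser reading, 8 of 16 do. In 4 of those 8 there is no plausible timing at all (T = 0), an implausible result for the strongest grade, so the natural reading is preferred.

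**Step 3: the same event against *Possibly*.** With K = 0, T = 1 and A = 0, four combinations remain (R and S free). All 4 meet *Possibly* on both readings. By Step 1 all 4 also meet *Unlikely*.

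**Step 4: extent of overlap.** Over all 32 combinations, *Unlikely* and *Possibly* are both met in 18 on the first reading of *Possibly* and in 10 on the second. Section 16.2 gives no order of precedence.

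**Step 5: is this only the re-challenge wording?** No. Without the re-administration limb, Step 1 still gives 16 of 16, because not K alone suffices. That limb has its own problem. The add-on is single use (Section 5.6.1) and Appendix B schedules one MCS colonoscopy, so no re-challenge is planned. If its absence is read as failure to reappear, all 16 combinations with R = 0 meet *Unlikely*. They include one (T = 1, K = 1, A = 0, R = 0, S = 1) that also meets *Related*.

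**Step 6: Section 16.1 beside Section 16.2.** The adverse device effect definition has no novelty condition, whereas *Related* in effect has one. The USADE definition has four routes: nature, incidence, severity and outcome. Only the nature route necessarily concerns a new type of event, so the tension is confined to that route.

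**Step 7: size per subject.** Enrolment is up to 47 (Section 11.1), and the safety set is all enrolled subjects (Section 15.2.3). One subject whose only device-related event is left out lowers the rate by 1/47 = 2.1 percentage points.

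**The case against.** The strongest reply is that *Possibly* remains open. Plausible timing is enough for its first limb, so a new injury is not forced into *Unlikely*, and an assessor who chooses *Possibly* satisfies the Section 4.6 threshold. This stands: the defect is an undetermined grade, not a fixed wrong one.

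Detection does not rest on the investigator's grade alone. Serious events go to the sponsor within 2 days and on to the DSMB within 72 hours whatever their relatedness (Section 16.3). The DSMB evaluates every adverse event (Sections 4.6 and 14.2) and judges relationship itself. Section 15.2.3 also reports the overall event rate and lists events individually with their relationship, so an event graded *Unlikely* stays visible. This stands too, although no other scale is given for the DSMB and nothing says whether it must use this one.

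A reader might infer three stronger points that the documents do not support:

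- *That the USADE category is defeated.* Section 16.1 names no Section 16.2 grade as its threshold, and unexpected incidence, severity or outcome of a known injury still qualifies.
- *That the device-related rate is necessarily understated.* Section 15.2.3 does not say which grades count; if *Possibly* counts and is chosen, nothing is lost.
- *That the chance of a new harm can be calculated from prior exposure to the latest version, in "two preliminary clinical studies including 30 subjects".* This would equate a known pattern with one already seen in those subjects. Section 4.2 lists perforation and laceration as potential device complications, although Section 4.7 reports no serious event or major complication in those studies. Knowledge also comes from the 35 pigs, the trials of other versions (Section 3.2) and the risk analysis.

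**Conclusion.** The point holds as a defect in a stated rule. On the natural reading of *Related*, an event new in nature cannot reach that grade. If its timing is plausible and it has no other cause, it meets *Unlikely* and *Possibly* at once, with nothing to decide between them. This fits poorly with the adverse device effect definition and with the nature route to a USADE, and it leaves open whether such a serious event reaches the Section 4.6 threshold.

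The effect on the secondary endpoint is conditional: 2.1 percentage points per affected subject at 47 enrolled, and only if *Related* alone counts or the overlap is resolved to *Unlikely*. The documents give no basis for estimating how often such an event would occur. The bar on *Related* depends on the natural parsing of AND/OR; the overlap between *Unlikely* and *Possibly* does not. The change should be made because the scale governs a safety endpoint and a study-level safety action, and correcting it needs only wording.

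**What to change.** In Section 16.2:

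1. Delete the known-pattern limb from *Unlikely*.
2. Make a known response pattern supporting, not required, evidence for *Related*, and bracket the mixed AND/OR conditions so that each definition has one reading.
3. Make the grades mutually exclusive by adding a rule such as: *an event with a reasonable temporal sequence and no more likely alternative cause is graded at least Possibly, whether or not it has been seen before with the device.* State that this rule takes precedence over the re-administration limb, and give the order in which the remaining grades are tested.
4. State that the DSMB uses the same definitions.
5. State which grades count as device related for Section 15.2.3 and for the ADE, SADE and USADE definitions in Section 16.1.

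The Section 4.6 rule itself need not change for this point. The cost is a wording amendment and matching CRF completion guidance, with no effect on sample size or visits. The downside is that the device-related rate may look slightly less favourable.

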##### **4.2. ANTICIPATED ADVERSE DEVICE EFFECTS**

The potential complications associated with the MCS device are:

- Perforation
- Laceration
- Mild tissue trauma
- Patient infection/biologic reaction

Several steps to mitigate those risks were made (see section 4.3) , following those mitigations the use of the MSC do not increase the risk to the patient.

However as the MCS is used in conjunction with a standard colonoscope during a colonoscopy procedure the complications associated with using the MCS cannot be differentiated from those associated with the colonoscopy procedure.

The risks associated with the colonoscopy procedure along with the procedure itself (i.e., preparation and sedation) as reported in the literature are:

- Colonoscopy-related risk such as bowel perforation, tissue trauma, abdominal pain, bleeding, fever, and infection.
- preparation related risks (lasting >24 hours following colonoscopy) are: Changes in bowel habits, Nausea and vomiting, Dehydration and Renal dysfunction (rare).
- Sedation-related are: cardiovascular disorder, hypotension, and hypoxia
- Death

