### 5.6. MCS ADD-ON DEVICE

#### 5.6.1. THE ADD-ON DEVICE

The MCS Add-on device is a single use disposable, which slips over a standard colonoscope with a maximum outer diameter of 21.2mm. The device consists of multiple irrigation and evacuation

conduits as well as channels for the sensing capabilities of the system. The Add-on device has an outer sleeve to provide a smooth surface while inside the colon and an inner sleeve to provide the proper connection to the colonoscope. At the distal end of the Add-on device is the insertion port for the colonoscope, which also includes an inflation connector that is attached to an air compressor. The insertion port is loaded into the loading fixture, which aids insertion of the colonoscope into the Add-on device. Proximal to the insertion port all of the add-on device's conduits branch off and extend to the WS cartridge [WSC]. The WS cartridge [WSC] is an integrated cartridge that connects the MCS Add-on device to the Workstation.

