### **Specific situations occurring during colonoscopy**

- If the attempt to reach the cecum is failed, the investigator shall perform the procedure with a pediatric or any other colonoscope he/she may choose without the MCS. The subject will complete the study as planned.
- If a medical condition requiring treatment is detected during colonoscopy, the subject will be treated as per the standard care.

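### The relatedness grades in 16.2 do not fit a device used once per subject: a perforation or laceration cannot reach Related, and can fit both Possibly and Unlikely

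*Combined protocol and SAP*

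**What the plan says.** Section 16.2 defines four grades.

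- *Unrelated*: the timing does not fit, and another cause is likely.
- *Unlikely*: any one of four conditions is enough. The last of them reads "OR does not reappear or worsen when the device is re-administered". The other three are that the timing does not fit, that another cause is likely, and that the event does not match a known device pattern.
- *Possibly*: "Any reaction that follows a reasonable temporal sequence from administration of study treatment OR that follows a known response pattern to the suspected device", together with the absence of a reasonable explanation from the subject's condition or another therapy.
- *Related*: timing and known pattern, "AND that recurs with re-challenge, AND/OR is improved by stopping the use of the device".

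On exposure, 5.6.1 states: "The MCS Add-on device is a single use disposable". Appendix B schedules one colonoscopy. If the cecum is not reached, 12.5 says "the investigator shall perform the procedure with a pediatric or any other colonoscope he/she may choose without the MCS".

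Section 4.2 has a list headed "The potential complications associated with the MCS device are", whose first two items are perforation and laceration. It adds that device complications "cannot be differentiated from those associated with the colonoscopy procedure".

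The grade is used in three places. Section 15.2.3 reports a device-related adverse event rate. Section 16.1 defines an ADE, and hence a SADE, by relation to device use. Section 4.6 halts the study pending the DSMB's investigation "in case of occurrence of a SAE at least possibly related to the MCS".

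**The concern.** Re-challenge and improvement on stopping are criteria for a treatment that is given repeatedly and can be withdrawn. Here the exposure is one procedure, and the structural injuries that the protocol itself anticipates leave no such evidence. The top grade is then closed to the events for which attribution matters most.

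The two middle grades also overlap. Two careful assessors could read 16.2 literally and grade the same perforation differently. Under one grade it counts towards the 4.6 halt, and under the other it does not. Section 15.2.3 does not say which grades count as device-related, so the reported rate and the ADE/SADE status of the event would depend on an unstated reading.

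**Working it through.** The plan gives no figure to reproduce, because the point concerns definitions. Each grade can be written as a logical rule and applied to one case.

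**Inputs.** T = timing fits. K = known device pattern. X = explained by the subject's condition or another therapy. R = recurs on re-challenge. D = improves on stopping. All five come from 16.2. For a perforation or laceration during the study procedure, T and K are true. R is false because no second exposure is planned (5.6.1, 12.5, Appendix B). D is false by clinical inference; the documents do not state it.

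**Rules and results.** The text leaves some groupings open, so each reading was tried.

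| Grade and reading | X false | X true |
|---|---|---|
| Related: T and K and (R or D) | No | No |
| Related: (T and K and R) or D | No | No |
| Related: T and K and R and D | No | No |
| Possibly: (T or K) and not X | Yes | No |
| Possibly: T or (K and not X) | Yes | Yes |
| Unlikely, re-administration condition counted as met | Yes | Yes |
| Unlikely, that condition treated as not applicable | No | Yes |
| Unrelated: (not T) and X | No | No |

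**What follows.**

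1. Related fails on every reading.
2. If the injury is unexplained, Possibly always holds. Unlikely also holds if an event that had no chance to reappear counts as not having reappeared.
3. If the colonoscopy is taken as another therapy that explains the injury, Unlikely holds on either treatment of the re-administration condition. Possibly then fails on one grouping and holds on the other. Section 4.2 says the two sources cannot be told apart, so the value of X is itself open.
4. The overlap is not confined to these injuries. An unexplained event with fitting timing but no known pattern meets Possibly (T is true) and Unlikely (K is false), without any use of the re-administration condition. Every Unrelated event also meets Unlikely.
5. With R always false, there are 2 × 2 × 2 × 2 = 16 combinations of T, K, X and D. If the re-administration condition is counted as met, all 16 satisfy Unlikely, including the 2 that satisfy Related on its first reading (T, K and D true, X either way).

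**Size.** Take one such event among the 47 planned subjects, all in the safety set.

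- Counted as device-related: 1/47 = 2.1%, exact 95% CI 0.05% to 11.3%.
- Not counted: 0/47 = 0%, exact 95% CI 0% to 7.5%.

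At the 0.35% major-complication rate for routine colonoscopy quoted in 14.2, the expected number is 47 × 0.0035 = 0.16, and the chance of at least one is 1 − (1 − 0.0035)^47 = 15.2%. Such an event would probably be single if it occurred at all, and its grade would settle the device-related serious event rate.

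**The case against.** **DSMB review.** A reader might infer that a device perforation could escape safety review. The documents do not support this. Sections 4.6 and 14.2 send every adverse event to the DSMB. Section 16.3 requires serious events to reach the sponsor within 2 days and the DSMB within a further 72 hours, whatever the grade, and has the DSMB judge relatedness itself. Only the automatic halt in 4.6 uses the grade, and 4.6 does not say whose grade governs.

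**Possibly is enough for 4.6.** This stands. An unexplained injury meets Possibly on both groupings, so losing Related does not by itself defeat the trigger.

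**Unlikely for every event.** A reader might infer that 16.2 sends everything to Unlikely. That needs the re-administration condition to count as met when it was never tested. The more natural reading is that it does not apply, and 16.2 does not say. The overlaps in items 3 and 4 of the working do not need that reading.

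**The colonoscopy as another therapy.** Section 16.2 grades relation to treatments or procedures, and 16.3 asks about the device and/or the study procedure. The colonoscopy is therefore not clearly an alternative explanation. This shows ambiguity, not a proven downward bias.

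**All four complications in 4.2.** A reader might extend the point to the whole list. The argument is made only for perforation and laceration. Mild tissue trauma and infection or biologic reaction may behave differently, and transient symptoms could meet the improvement condition.

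**Limited endpoint effect.** Section 7.2 does not mention relatedness, and 15.2.3 also reports the overall rate and lists every event, so no event disappears. That is correct, but 15.2.3 names a device-related rate and leaves it undefined.

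**Conclusion.** The point holds as a defect in the definitions. Under 16.2 a one-time structural injury cannot be graded Related, and it can fit both Possibly and Unlikely with no tie-break. At risk are the device-related rate in 15.2.3, the ADE/SADE classification in 16.1 (and with it the duty in 16.3 to reconsider the risk analysis after a SADE), and the automatic trigger in 4.6. For a single event the rate is either 2.1% or 0% of 47.

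This rests on three assumptions: no second exposure to the device, as the schedule implies; no improvement of a perforation or laceration on withdrawal, a clinical inference; and no other relatedness criteria elsewhere. The Serious Adverse Events Reporting Plan cited in 16.3 was not available and might contain some. The event in the size calculation is hypothetical, and no safety hypothesis test is affected.

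**What to change.** In 16.2 and on the adverse event form:

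1. Delete the re-challenge, re-administration and stopping conditions.
2. Define the four grades on timing, anatomical site and plausible mechanism, so that each event fits exactly one.
3. State in 15.2.3 that Possibly and Related both count as device-related, and say in 16.1 which grades make an event an ADE.
4. State whether the study colonoscopy counts as another therapy when grading.
5. Reconcile 16.2 with 4.2 and 4.6. How the halt should operate is for the sponsor and the DSMB to settle.

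A blanket rule that any event inseparable from the colonoscopy is at least possibly device-related should not be added as a matter of tabulation. Given 4.2, it would change how the 4.6 halt operates: at the protocol's 0.35% rate there is about a 15% chance of at least one major complication in 47 subjects even if the device adds no risk.

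The cost is wording in 16.2, 15.2.3 and 16.1 and on the form, with no change to design or sample size. The downside is a somewhat higher reported device-related rate.
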